**The Effect of The Mobile Application on Treatment Adherence, Self-Management, and
Quality of Life in Patients with Acute Myocardial Infarction Undergoing Primary
Percutaneous Coronary Intervention**

[name], [name],

[name], Msc, RN, Research Assistant (Corresponding author)

Department of Nursing, Trakya University Faculty of Health Sciences, Edirne, TURKIYE

Orcid No: [name]

e-posta: [contact]

[name] [name], Msc, RN, Associate Professor

Department of Nursing, Trakya University Faculty of Health Sciences, Edirne, TURKIYE

Orcid No: [name]

e-mail: [contact]

Address for Correspondence:

[name], Msc, RN, Research Assistant

Address: [name]

[contact]

[contact]

e-mail: [contact]

Background and Aim: Acute myocardial infarction is a clinical condition with high mortality and morbidity rates. Ensuring patient adherence to treatments and lifestyle recommendations after discharge is crucial for effective post-acute myocardial infarction management. This study aimed to determine the impact of the mobile application on treatment adherence, self-management, and quality of life in patients with acute myocardial infarction undergoing primary percutaneous coronary intervention.

Study's Methods

Study design and sample

The study was conducted as a prospective (6-month follow-up), two-group (control and intervention), randomized controlled, experimental study.

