The universe of the study consisted of patients who had their first time ST segment elevation MI (STEMI) undergoing PPCI in the Cardiology Clinic of a university hospital in Edirne, Turkey, between 01.11.2021 and 10.07.2024. In determining the sample of the study, power analysis was performed with reference to the study of Turan Kavradım and Özer (68). The effect size of the study was found to be 0.92 and considering this effect size, it was determined that it was sufficient to include a total of 54 patients, 27 in each group, at 95% power and 0.05 significance level. However, considering a 20% loss rate during the study period (30), it was aimed to reach a total of 66 patients, 33 patients for each group. Patients who volunteered to participate in the study were determined in accordance with the inclusion criteria. The selection of patients to the intervention and control groups was made using the simple randomization method. According to the randomization list, the groups were matched based on the time of discharge from the clinic of the patients. For patients who were discharged on the same day, the matching was based on their hospitalization times. The inclusion criteria were as follows: the patients who (1) had first time STEMI undergoing PPCI, (2) are over 18 years of age, (3) have a smartphone, (4) have internet access, (5) have orientation to place, time and situation, (6) have no problems with vision, hearing and speech, (7) are at least literate, (8) regularly come in for the doctor's check up, and (9) volunteer to participate in the study. Among the volunteers participating in the study, those who wanted to leave the study (2 patients) and those who didn't come in for the doctor's check up (3 patients) were excluded from the follow-up. Therefore, the study was completed with 61 patients, 30 in the intervention group and 31 in

the control group. The study design and implementation were based on the principles in the CONSORT (Consolidated Standards of Reporting Trials) list (Figure 1).

[figure not shown]

Figure 1. Flow chart of design and recruitment of participants according to CONSORT statement

Study Protocol

Education booklet

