In the third stage, a web page control panel was created that allows the mobile application to be controlled remotely, patient information to be viewed, data to be monitored, lifestyle information to be uploaded and viewed in the mobile application, personalized reminders to be sent to patients, and to be communicated with patients (<https://www.medicoll.com/>, <https://www.medicoll.com/brave/login>).

In the fourth phase, the application was purchased from Google Play Store and App Store. In the fifth stage, the mobile application and website were tested by experts for 1 week to determine usability of them and errors. Finally, a pilot study was conducted with 4 patients and the patients were allowed to use the application for a month. Patients who participated in the pilot study were not included in the study.

After the pilot study was completed, the Patient Information Form was filled out with all patients in the patient room before discharge. The researcher provided training to the patients in both groups in line with the education booklet and it was delivered to the patients. MEDIFOLL application was downloaded to the mobile phones of the patients in the intervention group and user registration was made. Information was provided to them on how to use the application and how to enter data such as blood pressure and pulse rate. The times of the use of medications prescribed during discharge were planned together with the patients and they were provided with the opportunity to enter their medications into the application.

Patients in the intervention and control groups were interviewed in the outpatient clinic 1 month, 3 months and 6 months after discharge, and the Patient Information Form, IUBÖ ve MIDAS scales were filled out. The flow chart of the research is presented in Figure 2.

Determination of the content of “Educational Booklet for Patients Who Have Had a Heart

Obtaining expert opinion for the educational booklet and developing the booklet

[figure not shown]

Figure 2. The flow chart of the research

Data collection tool

Patient Information Form: It, developed by the researcher through a literature review (15,18,30,36,59,67), consists of questions about the socio-demographic, the lifestyle, and the disease characteristics of the participants.

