Medical Adherence Report Scale (MARS): The scale was developed by Horne and Hankins to determine medication adherence in individuals with chronic diseases. The Turkish validity and reliability of the scale was performed by Şen et al. (21). The scale has 5 items, one sub-dimension and 5-point Likert type. The total score obtained from the scale varies between 5 and 25. A high total score indicates adherence to medication treatment, while a low score indicates non-adherence to medication treatment. The Cronbach alpha value of the scale was found to be 0.78 in the study of Şen et al. (21) and 0.68 in this study.

Myocardial Infarction Dimensional Assessment Scale (MIDAS): The Turkish validity and reliability of the scale, developed by Thompson et al., was performed by Yılmaz et al. (71). The scale is used to determine the HRQoL of individuals with MI and consists of 35 items and 7 sub-dimensions (physical activity, insecurity, emotional reaction, dependency, diet, concerns over medication, and medication side effects). This 5-point Likert-type scale is scored between 0-4. Scores that can be obtained from the scale and its sub-dimensions vary between 0-100. The score is calculated with the formula: (Total score obtained from the sub-dimension/highest score that can be obtained from the sub-dimension) x100. As the scores obtained from the scale increase, the perceived HRQoL worsens. In the study of Yılmaz et al. (71), the Cronbach alpha value of the sub-dimensions of the scale was found to be between 0.79-0.90. In this study, it was found to be 0.93.

Ethical Consideration

The study was conducted in accordance with the Declaration of Helsinki. The study protocol was approved by the Scientific Research Ethics Committee of XXX University Faculty of Medicine (xxx), and written permission was obtained from the institution where the study was to be conducted (xxx). Necessary written consents were obtained from the patients.

Data Analysis

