The data were evaluated using the IBM SPSS 22.0 (Statistical Package for Social Sciences 22.0) package program. The data to a normal distribution was examined by the Kolmogorov–Smirnov test. The number and percentage distribution were used to evaluate categorical data, and meanstandard deviation was used to evaluate continuous data. In the analysis of the data, Mann Whitney U test was used to compare the mean scores that did not show normal distribution between the groups and Student's t test was used to compare the mean scores that showed normal distribution. Pearson chi-square test and Fisher-Freeman-Halton Exact test analysis

were used to determine the relationship between groups for nominal variables. The statistical significance limit value was accepted as $p<0.05$.

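### No primary outcome, primary visit or multiplicity rule: two total scores tested at three visits at unadjusted p<0.05 would carry roughly an 11-26% false-positive risk, not 5%

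*Combined protocol and SAP*

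**What the plan says.** Background and Aim sets out to determine "the impact of the mobile application on treatment adherence, self-management, and quality of life", with no ranking among the three. Under Study Protocol, patients in both groups "were interviewed in the outpatient clinic 1 month, 3 months and 6 months after discharge", and at those visits the "IUBÖ ve MIDAS scales were filled out". No visit is marked as the deciding one. Under Data collection tool, MARS yields a total score, while MIDAS "consists of 35 items and 7 sub-dimensions", with 0-100 scores for the scale as well as for its parts. No separate instrument for self-management is described.

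The between-group analysis of scores in Data Analysis is a choice between two tests according to normality: Student's t test, or else "Mann Whitney U test was used to compare the mean scores that did not show normal distribution between the groups". One threshold covers everything: "The statistical significance limit value was accepted as $p<0.05".

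Study design and sample reports "The effect size of the study was found to be 0.92" without saying which outcome or visit it belongs to. The same section records that "the study was completed with 61 patients, 30 in the intervention group".

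**The concern.** A 5% significance level protects a conclusion only when it is clear in advance which test decides it. Here several scores at several visits may each be tested at 5%, and any of them could be presented as the trial's result. The real chance of claiming an effect when there is none is then the chance that at least one of these tests is significant.

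The power statement does not settle the matter. It describes a single comparison, and a reader cannot tell which one.

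**Working it through.** **Inputs from the documents.** Per-test level 0.05 (Data Analysis); visits at 1, 3 and 6 months (Study Protocol); one MARS total, one MIDAS total and 7 MIDAS sub-dimensions (Data collection tool); effect size 0.92, 27 per group, 95% power, and 30 and 31 completers (Study design and sample).

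**Assumptions.** IUBÖ is taken to be MARS, which the text never states. Each visit is taken to be tested separately. The documents give no correlations, so the assumed range is 0.3-0.9 between scores and 0.5-0.9 between visits.

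**The plan's own figure.** Exact noncentral-t power at d=0.92 with 27 per group uses 52 degrees of freedom and noncentrality 0.92 × √(27/2) = 3.38. One-sided power at 0.05 is 95.5%, which reproduces the stated 54 patients. Two-sided power is 91.3%, and a two-sided test would need 32 per group for 95%. Either way the calculation is for one test.

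**Number of tests.** Totals only: 2 scores × 3 visits = 6. With sub-dimensions: (2 + 7) × 3 = 27.

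**Independent tests.** P(at least one p<0.05) = 1 − 0.95^k.
- k = 6: 1 − 0.95^6 = 0.265
- k = 27: 1 − 0.95^27 = 0.750

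**Correlated tests.** Null trials were simulated 20,000 times per setting with 30 and 31 patients, normal scores, two-sided t tests at 0.05, and the MIDAS total built as the sum of its sub-dimensions. The last column is a separate check on the six tests using 1,000,000 multivariate-normal draws.

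| Correlation between scores / visits | 6 tests: any | 6 tests: favouring app | 27 tests: any | 27 tests: favouring app | 6 tests: any (check) |
|---|---|---|---|---|---|
| 0.3 / 0.5 | 22.6% | 11.5% | 61.0% | 33.3% | 23.0% |
| 0.3 / 0.7 | 20.4% | 10.1% | 55.5% | 29.6% | 20.1% |
| 0.5 / 0.5 | 22.5% | 11.2% | 53.2% | 27.8% | 21.9% |
| 0.5 / 0.7 | 19.6% | 9.7% | 47.2% | 24.5% | 19.2% |
| 0.7 / 0.7 | 17.7% | 8.8% | 37.5% | 18.9% | 17.6% |
| 0.9 / 0.9 | 11.2% | 5.8% | 19.5% | 9.9% | 11.6% |

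The nominal rates are 5% for any false result and 2.5% for one favouring the app.

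**Effect of Holm on the six tests.** In a separate null simulation, the chance of any false result was 4.3% (0.3 / 0.5), 3.7% (0.5 / 0.7) and 2.2% (0.9 / 0.9).

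**Power at d=0.92 with 30 and 31 patients.** Noncentrality is 0.92 × √(30 × 31/61) = 3.59 on 59 degrees of freedom.
- One two-sided test at 0.05: 94.2%
- One two-sided test at 0.05/6 = 0.0083: 80.2%
- Holm, per test: 80% if only one of the six effects is real, 82-83% if one scale is affected at all three visits, 87-90% if all six are real

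**The case against.** The strongest objection is that six tests is a reading, not a statement in the plan. Data Analysis lists no scores or visits, and the count needs IUBÖ to be MARS. That stands, so the figures are conditional. A different count would still not supply a primary outcome.

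The 11% end can also be challenged, because it needs correlations of 0.9 even between two different questionnaires. Data collection tool reports Cronbach alphas in this study of 0.68 for MARS and 0.93 for MIDAS. If alpha is read as reliability, the correlation between the scales is capped near √(0.68 × 0.93) = 0.80 and the visit-to-visit correlation of MARS near 0.68. With all correlations at these ceilings the six-test rate is about 14%. With visit correlations of 0.68 for MARS and 0.9 for MIDAS, and 0.3-0.5 between scales, it is 17-18%. This is a fair point, but it raises the low end.

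The six-test family could be called too narrow. The Patient Information Form, which covers lifestyle, is also completed at follow-up, and nominal variables are to be compared between groups. Any such tests would add to the inflation; they can be reported as exploratory.

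A joint model per scale across visits would cut the tests to about two. That is a reasonable alternative, but the plan does not contain it and it too would now be chosen after data collection. Two independent tests at 0.05 would still carry 1 − 0.95² = 9.75%.

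The 94% power baseline is for a two-sided test, whereas the stated sample size fits a one-sided one; one-sided power with 30 and 31 patients would be 97.2%. Sidedness is not stated and is a separate matter.

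Finally, the research flow chart is not shown, and the ethics-approved protocol and the study cited for the power analysis are outside these documents. Any of them might name a primary test, and the fix allows for that.

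**Conclusion.** The concern holds. The available text contains no primary outcome, primary visit, testing order, adjustment or joint model, and one 0.05 limit applies throughout. For the two totals at three visits, the chance of at least one false result is 26% if the tests are independent and 11-23% over the assumed correlations; the reported reliabilities make the upper part of that range more plausible than the lower. That is about two to five times the nominal 5%. A false result favouring the app has a chance of about 6-12%, against 2.5%. If the sub-dimensions are tested too, the corresponding figures are 20-61% and 10-33%, with 75% as the reference for 27 independent tests.

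These rates apply when there is no true effect on any score at any visit. They rest on the assumed test count, the reading of IUBÖ as MARS and the assumed correlations. The omission itself rests on none of these, and it must be fixed before any single score or visit is presented as the trial's result.

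**What to change.** - Check records dated before the data were seen, such as the ethics submission or the original power calculation. If one of them fixed a single primary outcome and visit, name that test as primary and cite the record.
- If none did, apply Holm across the six tests of MARS total and MIDAS total by visit, and state that this was decided after data collection. Do not choose a primary test now.
- In either case, report the seven MIDAS sub-dimensions, and any follow-up comparisons from the Patient Information Form, as exploratory with estimates and confidence intervals.
- State which outcome and visit the 0.92 refers to, and whether IUBÖ is MARS.

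The cost is a records check, an adjustment of six p-values and a few sentences in Data Analysis. No new data are needed. Under Holm, some nominally significant results may no longer support a claim, and two-sided power per test at d=0.92 falls from 94% to 80-90%.
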